#### 9.4. Six-Minute Walk Test

Six minute walk (6MW) distance, as performed at screening or within 6 months prior to screening. The subject is asked to walk along a prescribed path (typically 30 meters long) as far as possible during a 6-minute interval. The subject may walk at whatever pace is comfortable, with the goal of walking the longest distance possible. The subject may rest as needed. The subject will need to walk a minimum distance of  $\geq$  100 meters and maximum distance of  $\leq$ 500 meters to meet study inclusion criteria. The distance walked will be entered into the CRF.

## 9.5. Safety Assessments

Planned time points for all safety assessments are provided in the SoA (Section 2).

## 9.5.1. Physical Examinations

- A complete physical examination will include, at a minimum, assessments of the Skin, CV, Respiratory, Gastrointestinal and Neurological systems. Height and weight will also be measured and recorded (at screening only).
- A brief physical examination will include, at a minimum, assessments of the skin, lungs, CV system, and abdomen (liver and spleen).
- Investigators should pay special attention to clinical signs related to previous serious illnesses.

## 9.5.2. Vital Signs

- Pulse rate, respiratory rate, and BP will be assessed.
- Blood pressure and pulse measurements will be assessed (supine) with a completely automated device. Manual techniques will be used only if an automated device is not available.
- Blood pressure and pulse measurements should be preceded by at least 5 minutes of rest for the participant in a quiet setting without distractions (eg, television, cell phones). At screening there will be 1 pulse and 3 BP measurements (3 consecutive BP readings will be recorded at intervals of at least 1 minute). The average of the 3 BP readings will be recorded on the CRF.

## 9.5.3. Pulse Oximetry

• Oxygen saturation will be measured by pulse oximetry after the subject has been at rest for at least 5 minutes.

## 9.5.4. Electrocardiograms

- 12-lead ECG will be obtained using an ECG machine that automatically calculates the HR and measures PR, QRS, QT, and QTc intervals. Refer to Section 8.2 for QTc monitoring criteria and additional QTc readings that may be necessary.
- Triplicate ECG are required at screening and predose. At these time points, 3 individual ECG tracings should be obtained as closely as possible in succession, but no more than 2 minutes apart.

# 9.5.5. Telemetry

- Telemetry will be measured continuously as detailed in the SoA (Section 2).
- Only AE and SAE data related to telemetry will be databased.

## 9.5.6. Clinical Safety Laboratory Assessments

• Refer to Appendix 2 for the list of clinical laboratory tests to be performed and to the SoA (Section 2) for the timing and frequency.

- The investigator must review the laboratory report, document this review, and record any clinically relevant changes occurring during the study in the AE section of the CRF. The laboratory reports must be filed with the source documents. Clinically significant abnormal laboratory findings are those which are not associated with the underlying disease, unless judged by the investigator to be more severe than expected for the participant's condition.
- All laboratory tests with values considered clinically significantly abnormal during participation in the study or within 3 days after the last dose of study treatment should be repeated until the values return to normal or baseline or are no longer considered significantly abnormal by the investigator or medical monitor.
- If such values do not return to normal/baseline within a period of time judged reasonable by the investigator, the etiology should be identified and the sponsor notified.
- All protocol-required laboratory assessments, as defined in Appendix 2, must be conducted in accordance with the laboratory manual and the SoA.
- If laboratory values from non-protocol specified laboratory assessments performed at the institution's local laboratory require a change in participant management or are considered clinically significant by the investigator (eg, SAE or AE or dose modification), then the results must be recorded in the CRF.

#### 9.6. Pharmacokinetics

Whole blood samples will be collected for measurement of plasma concentrations of GSK2586881 as specified in the SoA (Section 2). The actual date and time (24-hour clock time) of each sample will be recorded.

Additional sample time points may be added during the study if warranted and agreed upon between the investigator and the sponsor, however, the maximum allowed blood volume will not be exceeded.

Samples collected for analyses of GSK2586881 plasma concentration may also be used to evaluate safety or efficacy aspects related to concerns arising during or after the study.

Once the plasma has been analyzed for GSK2586881 any remaining plasma may be analyzed for other compound-related metabolites and the results reported under a separate protocol.

Details of blood sample collection (including volume to be collected), processing, storage and shipping procedures are provided in the lab manual.

Plasma analysis will be performed under the control of GSK, the details of which will be included in the lab manual.

## 9.7. Immunogenicity Assessments

Whole blood samples will be collected for measurement of immunogenicity assessments as specified in the SoA (Section 2).

Additional visits at 12, 24, and 36 weeks post-dose (and less frequently thereafter), to obtain immunogenicity samples may be required in the unlikely event that subjects develop a clinically relevant immunoglobulin response to the drug as described in the lab manual.

Details of immunogenicity blood sample collection (including volume to be collected), processing, storage and shipping procedures are provided in the lab manual.

#### 9.8. Biomarkers

The following samples for biomarker research will be collected from all participants in this study as specified in the SoA (Section 2):

- RAS peptides Ang II, Ang (1-7) and Ang (1-5) and other vasoctive peptides in the RAS and bradykinin cascade, and Nitric Oxide may be analyzed from plasma as data permit.
- Biomarkers of disease activity: NT pro-BNP, and cardiac troponin I may be analyzed from serum as data permit.

Additional sample time points may be added during the study if warranted and agreed between the investigator and the sponsor, however the maximum allowed blood volume will not be exceeded

In addition, with the participant's consent, samples will be stored and may be used to investigate additional biomarkers thought to play a role in PAH disease progression or to evaluate their association with observed clinical responses to GSK2586881.

Samples may also be used for research to develop methods or support identification of prognostic/diagnostic biomarkers associated with clinical outcomes in PAH and related diseases.

Details of blood sample collection (including volume to be collected), processing, storage and shipping procedures are provided in the lab manual.

## 9.9. Genetics

A 6 mL blood sample for deoxyribonucleic acid (DNA) isolation will be collected from participants who have consented to participate in the genetics analysis component of the study. Participation is optional. Participants who do not wish to participate in the genetic research may still participate in the study.

In the event of DNA extraction failure, a replacement genetic blood sample may be requested from the participant. Signed informed consent will be required to obtain a replacement sample unless it was included in the original consent.

Appendix 6 for Information regarding genetic research. Details on processes for collection and shipment and destruction of these samples can be found in SRM.

#### 10. STATISTICAL CONSIDERATIONS

## 10.1. Sample Size Determination

The sample size chosen is not based on statistical considerations.

The design of the study is deemed acceptable under the anticipated safety profile, given previous clinical experience with GSK2586881.

If additional participants/cohorts are enrolled to allow for evaluation of additional dose levels the proposed analysis approach(s) would be modified accordingly.

## 10.2. Populations for Analyses

For purposes of analysis, the following populations are defined:

Population	Description	
Enrolled	All participants who sign the ICF	
Safety	All participants who take at least 1 dose of study treatment.  Participants will be analyzed according to the treatment they actually received.	
Evaluable	All participants who are in the Safety population who complete all Day 1 assessments (including up to 24 hours post dose) and were not deemed to have had major protocol deviations (as defined with the PDMP)	
PK Population	Subjects in the 'Safety' population for whom a PK sample was obtained and analysed. PK population will be the population for reporting PK data.	

## 10.3. Statistical Analyses

Limited subject level data/information from a GSK supported study (NCT01884051) is available at doses of 0.2 mg/kg and 0.4 mg/kg. This data may be used as supportive only in reference to basic comparisons of safety, PK and PD with the current study. This previous study data will not be incorporated into statistical analyses associated with the current study.

## 10.3.1. Pharmacodynamic and Safety Analyses

Endpoint	Statistical Analysis Methods		
Primary	Descriptive Summaries, Figures and Listings of Change from Baseline PVR, CO and mPAP by planned timepoints.		
	
 
If data permit, linear regression of Dose vs Change from Baseline PVR, CO and/or mPAP at 4 hours (endpoints loge transformed if necessary).
 
		
Secondary	Descriptive Summaries, Figures and Listings.		
	
 
Simple figures (e.g. scatterplots and/or scatterplot matrix plots)     exploring correlation between key PD endpoints (e.g. RAS peptides)     and the Primary endpoints (PVR, CO and mPAP).
 
		
	All safety analyses will be performed on the Safety Population		
Exploratory	Will be described in the RAP. Note that exploratory genetic analyses, should they occur will be detailed in a separate RAP.		

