#### 7.2. Dose Modification

The study will comprise of 4 separate cohorts. Participants will be administered a single dose of one of the following planned doses: 0.1, 0.2, 0.4, or 0.8mg/kg.

Dose escalation will occur after a minimum of 4 participants have been dosed per cohort and review of safety, tolerability, PK and hemodynamic data up to 24h post dose has taken place. Dose escalation will continue up to a maximum dose of 0.8mg/kg.

Cohort sizes may vary with a minimum of 4 participants per cohort. Additional participants may be enrolled to expand a dosing cohort to further evaluate findings at a given dose level.

If a subject experiences a dose limiting toxicity (DLT) that is considered at least possibly related to study drug, dosing of additional participants will be halted and a full safety review will be performed to confirm causality. If 2 participants in any cohort experience

a DLT considered at least possibly related to study drug, the maximum tolerated dose (MTD) has been exceeded.

Dose limiting toxicities are defined as toxicities that, due to their severity or duration, are considered unacceptable, and limit further dose escalation. Examples of DLT's include, but are not limited to:

- Severe headache unrelieved by nonsteroidal anti-inflammatory drugs (NSAIDS)
- Nausea/Vomiting
- Hypotension as defined by mean arterial pressure <60mmHg or a drop in systolic BP of 25%

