# 7.3. Method of Treatment Assignment

As this is an open label study, participants will be assigned to the ongoing treatment group at that time.

Study using IWRS	All participants will be assigned to a treatment group using an Interactive Web Response System (IWRS). Before the study starts, the log in information & directions for the IWRS will be provided to each site.
	Study treatment will be dispensed at the study visits summarized in SOA.

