## 10.3.3. Interim Analyses

Safety, PK and pulmonary hemodynamic data will be reviewed after 4 subjects have completed dosing in each cohort prior to dosing at the next level. A linear regression model may be fitted to the (log transformed, if necessary) Change from Baseline at 4h PVR, CO and/or mPAP data from the first three cohorts (Dose Vs baseline adjusted response); and the slope parameter estimated along with the (extrapolated) mean response for the planned 4th dose of 0.8mg/kg. This will be used in addition to safety, PK and other PD data, to aid the team in decision making with regards to additional subject recruitment at an optimum dose level(s).

The RAP will describe the planned interim analyses in greater detail.

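### The dose regression for PVR, CO and mPAP has no baseline term and no fixed scale, so on the raw scale baseline differences between small sequential cohorts add noise, and possibly bias, to the dose slope

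*Protocol*

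**What the plan says.** Section 10.3.1 of the protocol gives tables, plots and listings of change from baseline as the main presentation of the primary endpoints. It then adds "If data permit, linear regression of Dose vs Change from Baseline PVR, CO and/or mPAP at 4 hours", with endpoints log "transformed if necessary". No other dose-response model for PVR, CO or mPAP is named.

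Section 10.3.3 says the same regression may be fitted to the first three cohorts, labels it "Dose Vs baseline adjusted response", and estimates the slope and an extrapolated mean at 0.8 mg/kg. The result helps the team decide on further recruitment and dose level, together with safety, PK and other PD data. The section adds: "The RAP will describe the planned interim analyses in greater detail". That plan is not at hand.

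Section 7.2 sets four doses (0.1, 0.2, 0.4 and 0.8 mg/kg) and at least 4 participants per cohort. Section 5.2 caps completers at 27. Under section 7.3, "participants will be assigned to the ongoing treatment group at that time", so dose follows enrolment order. The schedule of activities takes hemodynamic measurements before dosing and at 1, 2 and 4 hours. Baseline is nowhere named as a covariate, and nowhere excluded.

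**The concern.** A change score subtracts baseline but can still depend on it. A drug that lowers PVR by a fixed percentage produces a larger absolute fall in a participant who starts higher, and measurement error in the pre-dose value also links change to baseline. If cohorts differ in baseline, part of that difference enters the dose slope.

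This design leaves room for such differences. Cohorts are small, filled in sequence and not randomised. Inclusion criterion 2 sets a floor for mPAP and no ceiling. There is no placebo arm. The slope and the extrapolated 0.8 mg/kg mean feed the decision on where to recruit further, so both their precision and any distortion matter.

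The log option does not settle this. It applies only when judged necessary, with no rule. Section 4 defines the endpoint itself as change from baseline, and section 10.3.3 attaches the log to that change. Read literally, this means the logarithm of a change, which is undefined when the value falls.

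**Working it through.** **Inputs.** From the protocol: the four doses, 4 per cohort (12 at the interim, 16 at the end) and the maximum of 27. Section 10.1 says the size has no statistical basis, so the plan has no figure to reproduce. Assumed, for PVR only: lognormal baseline with mean 8 WU and CV 50%; within-day CV 10%; the same proportional fall (10% or 20%) at every dose, so there is no true dose response. Where drift is modelled, the later cohorts start 25% higher.

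**1. Chance imbalance in baseline.** The fitted 0.8-versus-0.1 difference in baseline has SD 0.7/√Σ(d − d̄)², in units of the baseline SD.
- The dose mean is 0.375. The squared deviations sum to 0.2875, times 4 = 1.15.
- SD = 0.7/√1.15 = 0.65. The difference exceeds 0.5 SD in 44% of trials and 1 SD in 13%, even with no drift.
- With 27 participants (6/7/7/7) the SD is 0.50.
- Interim: the dose mean is 0.2333 and Σ(d − d̄)² = 4 × 0.04667 = 0.1867. Baseline projected to 0.8 mg/kg has SD √(1/12 + 0.5667²/0.1867) = 1.34.

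**2. Precision, no drift (simulation).**

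| Quantity, raw scale | Effect | SD, dose only | SD, dose + baseline |
|---|---|---|---|
| Final 0.8-versus-0.1 difference | 10% | 0.835 WU | 0.732 WU |
| Final 0.8-versus-0.1 difference | 20% | 0.921 WU | 0.653 WU |
| Interim predicted mean at 0.8 | 10% | 1.72 WU | 1.52 WU |
| Interim predicted mean at 0.8 | 20% | 1.89 WU | 1.38 WU |

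For the final fit the variance falls by 1 − (0.732/0.835)² = 23% and 1 − (0.653/0.921)² = 50%.

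**3. Bias if baseline drifts.**
- Final fit, upper two cohorts 25% higher, 10% effect: mean changes are −0.8, −0.8, −1.0 and −1.0 WU. The slope is (0.025 + 0.425)(−0.2)/0.2875 = −0.313 per mg/kg, times 0.7 = −0.22 WU. For a 20% effect it is −0.44 WU. With the covariate, simulation gives +0.09 and +0.08 WU.
- Interim fit, third cohort 25% higher, 10% effect: the slope is 0.1667(−0.2)/0.04667 = −0.714. The prediction at 0.8 is −0.867 − 0.714 × 0.5667 = −1.27 WU, against −0.87 WU for the flat effect at the overall mean baseline. For a 20% effect it is −2.54 against −1.73. With the covariate, simulation gives −0.70 and −1.60.

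**4. What the covariate costs.**
- No drug effect, with drift: error in the measured baseline attenuates the adjustment. Error variance is about 0.01 × (8² + 4²) = 0.8, against a true variance of 16, so the coefficient is about −0.8/16.8 = −0.048. The fitted baseline difference is 0.313 × 10 × 0.7 = 2.19 WU in the final fit, giving about +0.10 WU. In the interim fit it is 7.14 × 0.7 = 5.0 WU, giving about +0.24 WU. The change-score fit gives about 0 in both.
- Change unrelated to baseline, no drift: variance rises by about 6–8%. It rises more if baseline is also aligned with dose. With a 1 SD drift and 16 participants the slope SD went from 0.562 to 0.625, a variance ratio of 1.24.

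**5. Log-ratio scale.** The SD of the fitted difference is 0.092–0.093 without log baseline and 0.095–0.097 with it. Under the 25% drift the log ratio alone is unbiased. Adding log baseline introduces about +0.01 in the final fit and +0.02 to +0.03 in the interim fit.

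**6. Error rate as a yardstick only** (the protocol states no test). Residual SD of change is set at 0.6 baseline SD and the slope of change on baseline at −0.2 to −0.6. With no drift the dose-only model finds a false slope in 4.6–5.6% of trials. With a 1 SD drift the rate is 6.9–15.8% (16 participants) and 8.3–23.2% (27). With the covariate it is 4.2–5.6% in every setting; baseline in this set is measured without error.

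**The case against.** The opposing case is strong in parts.

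- A reader might infer that the plan ignores baseline. It does not: the change score subtracts each participant's own value. What is missing is baseline as a covariate.
- A reader might infer that the plan fixes absolute change. It does not: both sections allow a log transform, and a log ratio removes a purely proportional dependence. The gain in steps 2 and 3 belongs to the raw scale.
- A reader might infer that baseline differences will be taken for dose response. The documents do not support this. They do not say which cohorts preceded Amendment 4, and its changes to walk distance, BMI and eGFR limits are not changes in baseline PVR. Without drift there is no average bias, only noise.
- In non-randomised cohorts a covariate is not neutral. With drift and no drug effect it creates a small artefact that the change score avoids (step 4).
- The regression is optional, no test is stated, and the interim fit is one input among several. The reporting and analysis plan may name covariates.

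The first four points stand; they limit the claim and shape the remedy. The last lowers the stakes but does not remove the point, because the protocol itself names the model, labels its interim response as already adjusted for baseline, and uses it to inform recruitment by dose.

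**Conclusion.** The point holds as a matter of precision and of an incompletely fixed model, with moderate confidence. On the raw scale with a proportional effect of 10–20%, leaving baseline out costs 23–50% of the variance of the fitted dose difference. A 25% drift in baseline would add an artefact of −0.22 to −0.44 WU, about a quarter to a half of that difference's no-drift SD (0.22/0.835 = 0.26; 0.44/0.921 = 0.48). The interim extrapolation is more exposed: about −0.4 WU (10% effect) or −0.8 WU (20% effect) if the third cohort alone starts 25% higher. All of this rests on the assumed PVR distribution and was not computed for CO or mPAP. On the log-ratio scale the problem largely disappears, which is why the undefined log option matters as much as the missing covariate. The analysis is optional and supportive, so this is worth correcting but does not undermine the study.

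**What to change.** In sections 10.3.1 and 10.3.3:

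- **Raw scale:** add the participant's own pre-dose value of the same variable as a covariate. Report the dose slope and the predicted means, including the interim mean at 0.8 mg/kg, at the overall mean baseline.
- **Log scale:** define the response as log(4 h value / pre-dose value). Use log baseline only as a sensitivity analysis, since it brings no gain there. State in advance how the scale is chosen.
- **Wording and display:** define the interim response label to match. Show the unadjusted change-score fit beside the adjusted one, and state that dose is confounded with enrolment order, which neither fit removes.

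The cost is a few lines of text and one residual degree of freedom (14 to 13 with 16 participants, 10 to 9 with 12), with no new data. The downside is the variance loss and the small residual bias in step 4: about +0.1 WU in the final fit and +0.2 WU in the three-cohort fit under the stated assumptions.

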# 10.3.2. Pharmacokinetic and Pharmacokinetic-Pharmacodynamic Analyses

Pharmacokinetics analysis will be performed by, or under direct auspices of the Clinical PK Modeling & Simulation department within GSK. Plasma GSK2586881 concentration-time data will be analyzed by non-compartmental methods with WinNonlin V6.3 or greater. Calculations will be based on the actual sampling times recorded during the study.

From the plasma concentration-time data, the following PK parameters will be determined, as data permit: maximum observed plasma concentration (Cmax), time to Cmax (tmax), area under the plasma concentration-time curve [AUC(0-t) and area under the concentration-time curve from time zero (pre-dose) extrapolated to infinite time [AUC(0- $\infty$ )], the last observed quantifiable concentration (Clast), time of the last quantifiable concentration (tlast), plasma clearance (CL), volume of distribution (VD) and apparent terminal phase half-life (t1/2). Other PK parameters may also be determined.

Pharmacokinetic data will be presented in graphical and/or tabular form and will be summarized descriptively. All PK data will be stored in the Archives, GSK Pharmaceuticals, research and development (R&D).

A population PK analysis may be conducted. In addition the GSK2586881 plasma concentration-time data may be merged with historical data and analysed as part of a population PK meta-analysis. Further details will be provided in the RAP. If data permit, potential association between systemic exposure of GSK2586881 and identified biomarker (e.g. Ang II, Ang(1-7), Ang(1-5)), and/or clinical related endpoints (pulmonary vascular hemodynamic) may be studied. In addition the PK/PD data may be

merged with historical data and analysed as part of a population PK/PD (biomarker) meta-analysis. Further details will be provided in the RAP. Population PK and PK/PD exploratory analyses may be presented separately to the CSR.

